5 STUDY POPULATION CHARACTERISTICS

5.1 Participant disposition

The number of participants who signed the informed consent, participants who completed or prematurely discontinued the study, as well as the reason for discontinuation will be summarized for all participants, based on the All Study Participants. A participant who completed the study is defined as a study participant who completed all visits up to and including the EOT/EOS visit (in the Follow-up Period).

The number and percentage of study participants who discontinued due to AEs will be summarized separately for all study participants and per age group (adults and elderly).

The number and percentage of study participants included in each of the analysis sets will be summarized for all participants based on the All Study Participants. Percentages will be calculated based on the All Participants Set for the purpose of this summary.

Screening failure reasons will be listed for the All Study Participants. A listing of participants who did not meet study eligibility criteria will also be presented for the All Study Participants.

In addition, the following listings will be presented:

- Participant disposition (All Study Participants)
- Study discontinuation (FAS)
- Visit dates (FAS)
- Participant analysis sets (All Study Participants)

The listing of participant disposition will include the date of informed consent, date and time of first and last dose of study medication, date of premature termination and primary reason (if applicable) and date of final contact.

The listing of study discontinuation will include the reason for discontinuation and the number of days on study medication during the Period 1B (MD). During the Period 1A (SD), there was one day of study medication.

The number of days on study medication during the Period 1B (MD) will be calculated as follows:

$$\begin{aligned} & \text{Number of Days on study medication (Period 1B)} \\ &= (\text{Date of Last Dose Received} \\ & - \text{Date of First Dose Received during MB}) + 1 \end{aligned}$$

5.2 Protocol deviations

Important protocol deviations will be identified and classified by the deviation types in the IPD document (see also section 3.4).

A listing of all IPDs identified at the DEM will be presented for all participants based on the FAS and will include the deviation type and description. The number and percentage of participants in the FAS with IPDs will be summarized for all participants, per treatment period

(Period 1A, Period 1B, and whole treatment period) and for each deviation type. The denominator for the percentages will be the number of participants in the FAS.

6 DEMOGRAPHICS AND OTHER BASELINE CHARACTERISTICS

6.1 Demographics

A by-participant (study participant) listing of demographics will be presented based on the ES. This will include the year of birth, age (in years), sex, race, ethnicity, country, height (in cm), weight (in kg) body mass index (BMI, in kg/m²). The body weight will be the measurement obtained at Screening. Body mass index (kg/m²) is documented in the CRF.

All demographic characteristics (except for year of birth) will be summarized for all participants based on the FAS. The summary of age will include descriptive statistics and categorical summaries, the latter based on requirements for European Union Drug Regulating Authorities Clinical Trials (EudraCT) and clinicaltrials.gov reporting.

For the EudraCT reporting, the categories will include:

- 18 to <65 years
- 65 to <85 years
- ≥85 years

For clinicaltrials.gov reporting, the categories will include:

- ≤18 years
- 19 to <65 years
- ≥65 years

Additionally, the categories will include:

- 18 to <65 years
- 65 to <75 years
- ≥75 years

Characteristics on experience of medical or psychiatric condition and on experience of procedures or surgeries will be also summarized for the FAS.

6.2 Other Baseline characteristics

Lifestyle information (alcohol, tobacco, caffeinated beverage and illicit drug use), psychiatric and mental status (orientation, attention, memory, mood and calculus) and suicidality risk evaluation (C-SSRS) at Baseline will be listed and summarized for all participants in the FAS.

6.3 Medical history, procedure history and concomitant medical procedures

Medical history will be listed and summarized (in an incidence table) for the FAS for all participants, by MedDRA system organ class (SOC) and preferred term (PT). The reported term will be included in the listing. The summary will include the number and percentage of study participants, and will be sorted alphabetically by SOC and by descending incidence of PT within each SOC, based on the 'All Participants' column.

Procedure history (procedures or surgeries prior to study entry) will be listed separately by the procedure reported term based on the FAS.

Concomitant medical procedures occurring during the study will be listed for the FAS.

6.4 Prior and concomitant medications

Prior and concomitant medications (Period 1A (SD), Period 1B (MD) and overall) will be listed and summarized for all participants in the FAS, by WHODD Anatomical Main Group [Level 1 term text], Pharmacological Subgroup [Level 3 term text] and PT. The reported term will be included in the listing. Separate tabulations will be presented for prior medications and concomitant medications (Period 1A (SD), Period 1B (MD) and overall). Prior medications which continued into the treatment period will also be classified as concomitant and will be included in both summaries. Concomitant medications (Period 1A (SD), Period 1B (MD) and overall) will be described for all participants and by age group based on the FAS.

All tabulations will be sorted alphabetically by Level 1 term, alphabetical Level 3 term within Level 1 and decreasing frequency of PT in the 'All Participants' column.

6.4.1 Prior medication definition

Prior medications include any medications that started prior to the date of first dose of PSL. This includes medications that started prior to the first dose of PSL and continued after.

6.4.2 Concomitant medication definition

SD-Concomitant medications are medications taken anytime during Period 1A (SD) (Day 1 to Day 7).

MD-Concomitant medications are medications taken anytime during Period 1B (MD) and through the Follow-Up Period (Day 8 to Day 22).

If a medication is started prior to PSL administration and stopped after the first PSL administration (SD period), then that medication will be classified as both prior and SD-concomitant medication. If this medication is stopped during the Period 1B (MD) or later, then that medication will also be classified as prior, SD-concomitant and MD-concomitant medication.

Any medications with missing dates and/or times will be handled as described in [Section 4.2.4](#) to classify them as prior or concomitant.

7 MEASUREMENTS OF TREATMENT COMPLIANCE

The Investigator (or designee) is responsible for retaining all used, unused, and partially used containers of study medication until returned or destroyed.

A Drug Accountability form will be used to record study medication dispensing and return information on a by-participant basis. Compliance with the study medication is defined as consumption by the study participant that confirms 100% with the planned dosage.

Drug administration/consumption will be recorded and any discrepancies with the dosing regimen will be explained. Dosing deviations will be included in the listing of IPDs where applicable.

No formal calculations of compliance will be presented as all study medication is administered on site.

8 EFFICACY ANALYSES

Not applicable.

9 PHARMACOKINETICS

The calculation of the PK parameters of PSL and two of its metabolites () will be performed by the Pharmacokinetic Pharmacodynamic Modeling and Simulation Department, ICON PLC. All PK TELs will be produced by ICON PLC SAS programming (Early Phase).

Pharmacokinetic concentrations and PK parameters will be summarized using the PK-PPS and listed on the FAS by study participants. Figures of summaries will be based on the PK-PPS and figures of individual concentrations will be based on the FAS.

Pharmacokinetic parameters of PSL and two metabolites of PSL () will be computed using the actual sampling time points.

The plasma concentration-time profiles, urine amounts, and PK parameters of PSL and two metabolites of PSL () will be summarized by age group (adult [18-64 years] and elderly study participants [≥ 65 years]) and treatment period using descriptive statistics.

If PK effects by age group or gender as described in Section 4.10 observed, then the analysis of the primary PK variables will be repeated for subgroups within the adult and elderly cohorts.

Individual plasma PSL concentration-time profiles along with the individual plasma concentration-time profiles of the two metabolites of PSL will be displayed graphically on a linear-linear scale and semi-logarithmic scale (including spaghetti plots). Geometric mean plasma concentrations-time curves including 95% confidence intervals (CIs) will be displayed by cohort.

9.1 Analysis of the primary pharmacokinetic variables

Individual plasma concentrations of PSL will be listed and will include the actual and nominal sampling times and the deviation between them. All deviations will be calculated relative to the

last dose of study medication (on Day 1 for Period 1A (SD) and on Day 16 for Period 1B (MD)). Any samples that are obtained outside the tolerance window permitted at the specified time point will be discussed at the DEM and any possible exclusion from analysis will be documented accordingly. The primary PK variables in plasma used for PSL are: C_{max} , AUC_{0-t} , AUC for the single dose (Period 1A) and $C_{max,ss}$, and AUC_{τ} for the multiple dose (Period 1B). C_{max} and $C_{max,ss}$ will be determined from the observed concentration and time data. AUC_{τ} , AUC and AUC_{0-t} will be computed using the linear up/log down trapezoidal rule.

The PK plasma concentrations and the primary PK parameters of PSL and its metabolites will be summarized by nominal sampling times using descriptive statistics (number of available observations [n], arithmetic mean, median, standard deviation, minimum, maximum, geometric mean, geometric CV and 95% CI for the geometric mean [assuming log-normally distributed data]). Values below the LLOQ will be reported with a clear sign (flag variable in the dataset) indicating that they were below the LLOQ.

Individual participant concentration-time profiles of PSL and its metabolites will be displayed graphically in linear and semi-logarithmic scale. Combined individual (spaghetti) plots will be displayed by age group and analyte with all participants overlaid on the same plot (linear and semi-logarithmic scale).

Geometric mean profiles of plasma concentrations for PSL over time will be presented, with all treatment group overlaid on the same plot, in both linear and semi-logarithmic scale. For the linear scale plot only, the lower and upper 95% confidence interval (CI) for the geometric mean will be displayed.

All plasma concentration figures will include the LLOQ on the semi-logarithmic scale plots and will be based on scheduled times.

For the single dose (Period 1A) and multiple dose (Period 1B)) periods of the study, primary PK parameters (Single dose C_{max} , AUC_{0-t} , AUC and multiple dose: $C_{max,ss}$, AUC_{τ}) will be assessed in adults and elderly study participants with analysis of variance (ANOVA). Point estimates for the ratio of geometric means between adults and elderly study participants (and per category, if deemed necessary), and the respective 2-sided 90% CIs, will be computed using the least squares means and the root mean squares of error from the ANOVA of the log-transformed data with subsequent exponential transformation. Inter-participant variability on PK parameters will be derived from these analyses.

9.2 Analysis of secondary pharmacokinetic variables

The secondary PK variables are the amount excreted and metabolic ratio of amount excreted, measured in the urine PK of PSL and its metabolites. These PK variables along with urine concentrations and urine volume will be summarized for PSL and its metabolites by nominal sampling times using descriptive statistics (number of available observations [n], arithmetic mean, median, standard deviation, minimum, maximum, geometric mean, geometric CV and 95% CI for the geometric mean [assuming lognormally distributed data]). Values below the LLOQ will be reported with a clear sign (flag variable in the dataset) indicating that they were below the LLOQ.

9.3 Analysis of other pharmacokinetic variables

The other PK parameters and their analysis are the following:

- The relationship between PK parameters (AUC_t, AUC, AUC_{0-t}, CL/F, CL_R and t_{1/2}) of PSL and two metabolites of PSL and creatinine clearance, age (numerical), hepatic laboratory parameters (e.g., bilirubin, ALT, and AST) will be evaluated. The relationship will be displayed graphically using scatterplots, and the correlation between the PK parameter and the hepatic function test or age will be evaluated using linear regression, considering the PK parameter as the dependent variable and the hepatic function test or age as the independent variable.
- The point estimate and the 95% CI for the median differences for t_{max} between the adult and elderly cohorts will be computed according to the Hodges-Lehmann method.

10 SAFETY ANALYSES

All safety summaries and listings will be performed using the FAS. All safety variables will be summarized by the age group (adult and elderly study participants) and Treatment Period (SD, MD, and overall). Unless stated otherwise, all summaries including figures will be presented as detailed in the shells for figures. Summaries for continuous variables by time points will be based on the averaged value. Categorical variables will be summarized.

10.1 Extent of exposure

All study medication administration details will be listed by study participant. The listing will include the date and time of administration of the morning and evening dose and total daily dose of medication.

Exposure data will be listed only.

10.2 Adverse events

All AEs will be coded using the MedDRA[®] and characterized as pre-treatment, SD-treatment-emergent and MD-treatment-emergent according to the intake of the study medication.

- Adverse events with a start date prior to the first dose of study medication will be defined as pre-treatment AEs.
- SD-treatment-emergent AE (SD-TEAE) is defined as any AE with a start date/time on or after the first dose of study medication and until Day 7 (last Day of Period 1A) or any unresolved event already present before administration of study medication that worsens in intensity following exposure to the SD-treatment.
- MD-treatment-emergent AE (MD-TEAE) is defined as any AE with a start date/time on or after the first dose of study medication during the Period 1 B (usually on Day 8) and until 168 hours after the last PSL intake or any unresolved event already present before

administration of study medication during Period 1B that worsens in intensity following exposure to the MD-treatment.

Where dates are missing or partially missing, AEs will be assumed to be SD-treatment-emergent and MD-treatment-emergent, unless there is clear evidence to suggest that the AE started prior to the first dose of study medication. Missing or partially missing dates for AEs will be handled as described in [Section 4.2.4](#).

All AEs starting after the first intake of PSL through Day 7 will be attributed to SD-Treatment Emergent AEs; all AEs starting (strict) after Day 7 (the first PSL intake during Period 1B is foreshen on Day 8) through Day 22 will be attributed to MD-Treatment Emergent AEs and AE starting more than 168 hours post last dose of PSL will be attributed to the FU period.

All AEs will be recorded in the Case Report form (CRF) from the time of informed consent until study completion or termination. All AEs will be coded (see [Section 3.8](#)) and categorized by intensity (mild/moderate/severe) and relationship (related/not related) to study drug PSL as judged by the Investigator.

The number and percentage of participants who experience SD-TEAEs and MD-TEAEs will be summarized by MedDRA SOC, PT. The occurrence and incidence of AEs will also be summarized by intensity and relationship to PSL. Adverse events leading to discontinuation and SAEs will also be summarized.

Summaries of TEAEs (SD-TEAEs and MD-TEAEs) will include the following:

- Incidence of TEAEs (overview including number and percentage of participants with any TEAEs, serious TEAEs, TEAESI, discontinuations due to TEAEs, drug-related TEAEs, severe TEAEs, all deaths (AEs leading to death regardless of treatment emergence) and TEAEs leading to death; event counts will also be included)
- Incidence of TEAEs
- Incidence of TEAE of special interest
- Incidence of TEAEs by relationship
- Incidence of TEAEs by maximum relationship
- Incidence of TEAEs by intensity
- Incidence of TEAEs by maximum intensity
- Incidence of non-serious TEAEs above reporting threshold of 5% of participants
- Incidence of non-serious TEAEs above reporting threshold of 5% of participants by relationship

Summary tables will contain counts of study participants, percentages of study participants in parentheses and the number of events where applicable. A participant who has multiple events in the same SOC and PT will be counted only once in the participant counts but all events will be included.

In summaries including relationship, the following relationships will be summarized: 'Not related', 'Related'. Participants who experience the same event multiple times will be included in the most related category for tabulations by maximum relationship. Events with missing relationship will be considered as 'Related' but recorded as missing in the listings.

In summaries including intensity, the following intensity categories will be summarized: 'Mild', 'Moderate', 'Severe'. Participants who experience the same event multiple times will be included in the most severe category for tabulations by maximum intensity. Events with missing intensity will be considered as 'Severe' events for summary purposes but recorded as missing in the listings.

Incidence of Non-Serious TEAEs above reporting threshold of 5% of participants and incidence of Non-Serious TEAEs above reporting threshold of 5% of participants by relationship will be reported by system organ class and preferred term.

Adverse event summaries will be ordered alphabetically by SOC and decreasing frequency of PT within SOC in the group column for tables including event counts. For tables including only number and percentage of study participants, summaries will be ordered alphabetically by SOC and decreasing incidence of PT within SOC in the group column. A listing for all AEs will be presented by study participant and will include the onset date/time and outcome date/time of the event (including relative days), the AE duration (derived), time to onset (derived), pattern of event, intensity, relationship, action taken and outcome. In addition, the listing will flag AEs that led to discontinuation, TEAEs, AESIs and SAEs.

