4.2.4 Dates and times

Partial dates may be imputed for the following reasons:

- Classification of AEs as treatment-emergent
- Classification of medications as prior or concomitant

Imputed dates will not be shown in the listings; all dates will be displayed as reported in the database.

The following rules will be applied for partial start dates:

- If only the month and year are specified and the month and year of the first dose of study medication is not the same as the month and year of the start date then use the 1st of the month, or the date of screening if this is later (if the latter imputation results in an end date that is earlier than the start date, then use the 1st of the month). If time is missing this will be imputed as 00:00h
- If only the month and year are specified and the month and year of the first dose of study medication is the same as the month and year of the start date, then the date of the first dose of study medication will be used. If this results in an imputed start date that is after the specified end date, then use the 1st of the month, or the date of screening if this is later (if the latter imputation results in an end date that is earlier than the start date, then use the 1st of the month). If the imputed date is the date of dosing then time will be imputed as the start time of the dosing (i.e., event will be regarded as treatment-emergent)
- If only the year is specified, and the year of the first dose of study medication is not the same as the year of the start date then January 01 will be used. If time is missing this will be imputed as 00:00h
- If only the year is specified, and the year of the first dose of study medication is the same as the year of the start date, then the date of the first dose of study medication will be used. If this results in an imputed start date that is after the specified end date, then January 01, or the date of screening if this is later will be used (if the latter imputation results in an end date that is earlier than the start date, then January 01 will be used). If the imputed date is the date of first dose of study medication then time will be imputed as the start time of the study medication intake (i.e., event will be regarded as treatment-emergent)

The following rules will be applied to partial stop dates:

- If only the month and year are specified, then use the last day of the month
- If only the year is specified, then use December 31 of the known year

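### SAP 10.2 gives incompatible rules for assigning adverse events to the single-dose, multiple-dose or follow-up period, with no order of precedence

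*SAP*

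**What the plan says.** SAP 10.2 contains four statements that bear on the period of an AE.

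- **Definitions.** An SD-TEAE is "any AE with a start date/time on or after the first dose of study medication and until Day 7". An MD-TEAE starts at or after the first Period 1B dose and runs "until 168 hours after the last PSL intake". Each definition also takes in an unresolved earlier event that gets worse on treatment.
- **Missing or partial dates.** "AEs will be assumed to be SD-treatment-emergent and MD-treatment-emergent", with one exception: "unless there is clear evidence to suggest that the AE started prior to the first dose of study medication".
- **Cross-reference.** The next sentence reads "Missing or partially missing dates for AEs will be handled as described in" and points to 4.2.4. If the known month and year, or year alone, match those of the first dose, 4.2.4 says "then the date of the first dose of study medication will be used". If the month differs, the rule is to "use the 1st of the month, or the date of screening if this is later".
- **Attribution paragraph.** Every AE that starts after Day 7 "through Day 22 will be attributed to MD-Treatment Emergent AEs", with no condition that a Period 1B dose was taken. The same sentence places onsets more than 168 hours after the last dose in FU.

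Protocol 9.3.2 does not settle the matter. It separates pre-treatment from treatment-emergent AEs and asks for summaries by age group and period (SD, MD and overall).

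**The concern.** The definitions are anchored to doses and the attribution paragraph to calendar days. Where the two part, an event can fall in no period, in one, or in two. The two sentences on incomplete dates likewise give different answers for the same record.

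Incidence of TEAEs is a secondary safety variable (SAP 2.2.2.1). SAP 10 tabulates it by age group and period in cohorts planned at 10 and 18. Two programmers who each follow the text could produce different period tables. Otherwise the choice would be made at programming, with open-label data in view.

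**Working it through.** The plan gives no figure on this point to reproduce, so the check sets the windows side by side.

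**Inputs.** Single dose on Day 1 at about 08:00; later doses at about 08:00 and 20:00; last planned dose on the evening of Day 16 (SAP 3.2.2). One dose is enough to enter the FAS, on which safety is analysed (SAP 3.5.2), so a participant with only the single dose is included. Planned sizes are 10 adults and 18 elderly (SAP 2.4).

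**End of the 168-hour window.** 168 h / 24 = 7 days.

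- Completer: Day 16 20:00 + 7 days = Day 23 20:00.
- Early stopper, for example last dose Day 10 20:00: + 7 days = Day 17 20:00.
- Single dose only: Day 1 08:00 + 7 days = Day 8 08:00.

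**Classification of onsets.**

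| Onset | Definitions | Attribution paragraph |
|---|---|---|
| Completer, Day 8 after the dose to Day 22 | MD | MD |
| (a) Day 8, 00:00 to about 08:00, before the first Period 1B dose | neither | MD |
| (b) Single dose only, Day 9 | not MD | MD and FU |
| (b) Last dose Day 10 20:00, onset Day 19 | not MD | MD and FU |
| Completer, Day 23 before 20:00 | MD | unassigned |

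Case (a) needs no withdrawal and no missing date. Protocol Table 1-2 schedules a full physical examination, pre-dose laboratory tests and a pre-dose ECG on Day 8, and clinically relevant examination and laboratory findings become AEs (Protocol 8.3.1 and 8.3.4).

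**(c) Partial dates.** Suppose only month and year are known. If they match the first dose, 4.2.4 sets onset to Day 1, which is SD only. If the month is the next one, the result depends on the calendar. In a 30-day month:

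- First dose on the 28th: the 1st of the next month is Day 4, so SD, even if the true onset was the 8th (Day 11).
- First dose on the 20th: the 1st is Day 12, so MD.

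Either way 4.2.4 gives one period, where the preceding sentence of 10.2 gives two.

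To see which way 4.2.4 leans, take every first-dose date in a 365-day year with every true onset on Days 8 to 22: 365 × 15 = 5,475 combinations. Of these, 2,955 are set to Day 1 and 1,080 to the 1st of the next month but still by Day 7. So (2,955 + 1,080) / 5,475 = 4,035 / 5,475 = 74% go to SD. This assumes uniform dates and no conflicting stop date. It shows a direction and is not an expected error rate.

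**Size.** One participant is 1/10 = 10.0 points in adults and 1/18 = 5.6 points in the elderly. These are maxima: SAP 10.2 counts a participant once per term, so the change is zero if that participant already has the term in the period.

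**The case against.** The strongest reply has four parts.

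- **Counting in both periods looks deliberate.** It is a worst-case convention like those later in 10.2, where a missing relationship becomes related and a missing intensity becomes severe. It is also the only classification rule for a wholly missing start date, which 4.2.4 does not cover. This stands: the convention is not a fault in itself. The conflict is confined to partial dates, where the next sentence gives a different answer.
- **The FU clause can be read as overriding the Day 22 clause.** That would agree with the MD definition. It is a sensible reading, but the SAP does not state it, and the sentence as written assigns the event twice.
- **Exposure is small.** Case (a) covers about eight hours. AEs are recorded until completion or termination, and those who withdraw are asked back as soon as possible after the last dose. Fully dated onsets in completers are classified alike from the Day 8 dose to Day 22. All of this stands and limits the number of events.
- **The secondary variable is defined without a period split.** This is true, but Protocol 9.3.2 and SAP 10 both require the tables by period.

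**Conclusion.** The point holds as an inconsistency to correct, of limited practical size. The rules conflict in three situations: (a) the pre-dose hours of Day 8; (b) onset more than 168 hours after the last dose but by Day 22, in an early stopper or after the single dose only; and (c) partial onset dates. The maximum effect is 10.0 or 5.6 points per reassigned participant, assuming the planned group sizes, FAS denominators and nominal dose times.

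A reader might infer more than the documents support:

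- **That overall TEAE incidence is inflated.** Counting an event in both periods adds no participant to the overall summary. In (a) and (b) the issue is different: the definitions put the event in neither window, so whether it enters an overall total built from the two windows depends on the rule chosen.
- **That every affected event moves incidence by the full 10.0 or 5.6 points.** Those are ceilings.
- **That a participant who took only the single dose is simply counted as MD.** For a dated onset after 08:00 on Day 8, the same sentence also sends the event to FU.
- **That 4.2.4 always yields SD.** It leans that way but can yield MD.
- **That any event appearing in both periods is an error.** One that starts in Period 1A and worsens in Period 1B properly belongs in both.

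**What to change.** Delete the calendar-day attribution paragraph in SAP 10.2 and use one dose-anchored rule:

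- **SD-TEAE:** onset at or after the Day 1 dose and before the first Period 1B dose; if no Period 1B dose was taken, up to 168 hours after the Day 1 dose.
- **MD-TEAE:** at least one Period 1B dose taken, with onset at or after the first such dose and within 168 hours of the last dose.
- **FU:** any later onset.
- **Worsening:** keep the existing clause in both definitions.
- **Incomplete dates:** use 4.2.4 only to separate pre-treatment from treatment-emergent events, because its single imputed date leans to SD. If the known date parts and the stop date leave both periods possible, or the start date is wholly missing, keep the conservative count in both periods, but only for participants who took a Period 1B dose. For the others, count SD only. Count the event once in the overall summary.

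The cost is SAP wording, through the amendment that SAP section 1 requires when definitions change before database lock. No data collection changes. The small downside is that an event with an uncertain date can still appear in both period tables.
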